8.4 WITHDRAWAL CRITERIA AND PROCEDURES

Subjects may voluntarily withdraw consent at any time during the clinical trial with no loss of benefit or penalty. Subjects will be exempt from follow-up after withdrawing from the clinical trial. For subjects consented but have withdrawn, the trial site must retain the subject's informed consent and all documents pertaining to the subject prior to the subject's withdrawal.

The Investigator may withdraw any subject due to any of the following conditions:

1. Participation in the clinical trial may be contrary to the subject's current medical treatment, based on new information or changes in the subject's medical condition.
2. Any anatomical findings that would determine subject not suitable for implant with the Edwards aortic valve, Model 11000, which are discovered, intra-operatively. These may include findings such as:
 - a. The position of the coronary ostia relative to the Edwards aortic valve, Model 11000 would result in obstruction of blood flow,
 - b. the subject is hemodynamically unstable during the procedure requiring the procedure to be aborted prior to implanting the trial device,
 - c. A device is not available in the correct size for the subject;

The Investigator will document the withdrawal of trial subjects and notify the Trial Sponsor within five (5) working days. Additional subjects will be screened to replace those subjects who are withdrawn by the Investigator during the surgical procedure prior to implant.

Edwards will inform the Investigator of any new information about the trial that may affect the health, safety or welfare of the subjects or that may influence subject's decision to continue participating in the trial.

⁴ Note: Previously implanted means that the index aortic valve replacement procedure was completed. The procedure is complete when the surgeon takes the subject off cardiopulmonary bypass and restarts the heart.

9 STATISTICAL METHODS

9.1 SAMPLE SIZE

Up to 200 subjects will be enrolled in the trial at up to 6 participating sites.

9.2 ANALYSIS POPULATION

The analyses of safety data will include all enrolled subjects. Subjects are considered enrolled in the clinical trial after meeting the enrollment criteria, signing the informed consent and the surgeon determines that the index valve can be implanted.

The analyses of performance data will include the index valve population, defined as all subjects that are enrolled into the trial and that are implanted with the index valve.

9.3 SAFETY ANALYSIS

Early adverse events within 30 days of procedure will be reported as the number of events divided by the number of enrolled subjects. Linearized rates will be used to summarize adverse events for the late (>30 days) post-operative period. The linearized rates will be calculated as the number of late events divided by the total number of late-subject years.

Percentages for the early events and linearized rates for the late events also will be calculated for all other complications observed in the trial.

Actuarial rates based on the method of Kaplan-Meier will be calculated for each of the safety endpoints at each of the follow-up time points.

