7.3 ENDPOINTS

7.3.1 SAFETY ENDPOINTS

Descriptive information of early rates and late linearized rates of the following:

- Structural valve deterioration
- Thromboembolism
- All bleeding/hemorrhage
- Major bleeding/hemorrhage
- All paravalvular leak
- Major paravalvular leak
- Non-structural valve dysfunction
- Endocarditis
- Hemolysis
- All cause mortality
- Trial valve-related mortality
- Explant

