10.7 MISSED SUBJECT VISITS

The Investigator(s) will make every attempt to follow the subjects and subjects will be encouraged by the Investigator(s) to report any address or telephone number changes to the trial site. They will also be informed of the importance of returning for scheduled follow-up visits even if they are not having any problems.

If a subject cannot be reached for a follow-up visit, the Investigator will document on the CRF, the efforts undertaken to contact the subject or the subject's primary health care provider. These efforts should include 2 attempts of telephone contact at separate dates and times, and a registered letter before the end of the follow-up window. If a subject cannot be reached for a follow-up visit, or misses a scheduled visit, the visit will be recorded as a missed visit on the date of last attempted contact. Subjects who miss a visit will not be considered withdrawn. At the next visit interval, the Investigator and/or designee will attempt to contact the subject again for follow-up. Should this attempt to contact the subject fail, a family member should be contacted in addition to the subject. Subjects who miss 2 sequential follow-up visits will be considered lost to follow-up at the second missed visit and exempt from further trial follow-up. After the subject is terminated from the trial, the Investigator will attempt to determine if the subject is alive, including searching national mortality registries as permitted by local laws.

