10.8 TRIAL SUBJECT EXIT

Trial Subjects exit the trial when no additional follow-up visits, procedures, or data collection are required. A subject is exited from the trial in the following instances:

- Subject fails enrollment criteria after written consent
- Subject is considered enrolled as "intent to treat" however surgeon is unable to complete the implant procedure*
- Subject has trial device explanted*
- Subject is lost-to-follow-up
- Subject withdraws from the trial
- Subject death
- Subject completes trial follow-up

* Subjects will be followed for 30 days or until any adverse events experienced by this cohort are resolved and then will be exited from the trial.

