Did the surgical procedure occur at the investigational center? No Yes

Please indicate the type of procedure that was performed:

If Valve-in-valve replacement or Other is the type of procedure that was performed, please answer questions at the bottom of the next page

EXPLANT

When was the device explanted?

Was information collected about the explant procedure? No Yes

What was the surgical approach used for the explant procedure?

What type of aortotomy was performed?
(Enter Type or Not Available)

Were study valve leaflets removed? No Yes Not Available

Was study valve sewing ring removed? No Yes Not Available

Ease of study valve explant (Rate ease on a scale of 1-5, 5 being the best)

1 2 3 4 5 N/A

Additional comments:

Was a replacement valve implanted? No Yes

Please provide the following information about the replacement valve:

Manufacturer and model:

Size (mm):

Subject ID

Site

Visit Date

Status

Visit Name

AE

Subevent#

CRF Name

REOPERATION

Blank CRF

Was information collected about the appearance of the valve prior to or immediately following explant? No Yes

Please indicate whether the following conditions were observed:

- No Yes Thrombus
- No Yes Vegetation
- No Yes Suture interference
- No Yes Calcification
- No Yes Fibrosis
- No Yes Dehiscence

Other observations

[Empty text box for other observations]

Did excision of the study valve require or result in structural changes?

- No Yes Not Available

Please specify:

[Empty text box for specifying structural changes]

Was the explanted study valve returned? No Yes

RGA #

[Empty text box for RGA #]

VALVE-IN-VALVE REPLACEMENT

Please provide the following information about the replacement valve:

Manufacturer and model:

[Empty text box for manufacturer and model]

Size (mm):

[Empty text box for size]

OTHER

Please specify:

[Empty text box for other replacement valve information]

STUDY EXIT

Version A

Date of Study Exit: (DD/MMM/YYYY)

Please indicate the reason for study exit:

Please indicate when the subject withdrew:

Please indicate the reason for withdrawal:

Date of Death: (DD/MMM/YYYY)

Did the subject die intraoperatively during the study procedure? No Yes

Did the subject die prior to discharge from the hospital after the study procedure? No Yes

Please provide the following information about the subject's hospitalization after the study valve procedure

Duration of time in the Intensive Care Unit (ICU)

Days: and Hours:

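### Must Section 9.3 state when late-mortality time at risk ends, and whether deaths found after study exit count?

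*Combined protocol and SAP*

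**What the plan says.** Section 9.3 fixes the start of the late period and the form of the rate: "Linearized rates will be used to summarize adverse events for the late (>30 days) post-operative period", and "The linearized rates will be calculated as the number of late events divided by the total number of late-subject years". It adds that "Actuarial rates based on the method of Kaplan-Meier will be calculated for each of the safety endpoints at each of the follow-up time points". It states neither an end of time at risk nor a censoring rule. "All cause mortality" is one of the safety endpoints listed in Section 7.3.1.

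Section 10.7 deals with loss: "Subjects who miss 2 sequential follow-up visits will be considered lost to follow-up at the second missed visit and exempt from further trial follow-up". A missed visit takes the date of the last contact attempt. The section continues: "After the subject is terminated from the trial, the Investigator will attempt to determine if the subject is alive, including searching national mortality registries", so far as local law allows. Section 10.8 describes exit in operational terms, "Trial Subjects exit the trial when no additional follow-up visits, procedures, or data collection are required", and lists loss to follow-up and death among the reasons. Section 9.6 says that analyses use whatever valid data are available and that nothing is imputed.

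In Appendix 15.3 the Study Exit form has fields for the exit date and the date of death. The deviation forms for the 3-month and yearly visits ask whether family or friends were contacted, when, and whether the subject was alive. They also ask whether survival can be confirmed from another source.

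**The concern.** A rate per subject-year is sound only if deaths and time stop at the same point. Section 9.3 names no such point, and Section 10.7 produces information on deaths after the subject has formally left. If post-exit deaths were counted while survivors' time stopped at exit or earlier, the rate would be too high. If pre-exit deaths that came to light late were left out while time ran to exit, it would be too low. Section 9.6 could be read as admitting any death that becomes known, so it does not settle the matter.

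The interval is not trivial. A lost subject exits at the second missed visit, nominally 1 to 2 years after the last one attended. With the Table 7 windows it can reach 2.5 years: seen at year 2 minus 3 months (1.75), second miss at year 4 plus 3 months (4.25). At stake is whether the reported late mortality depends on an unwritten choice.

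**Working it through.** **The plan's own figure.** There is none to reproduce. The documents give no mortality rate, loss rate or subject-years. What follows applies the Section 9.3 ratio to assumed inputs.

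**Inputs from the plan.** N = 200 (Section 9.1, an upper limit); late time starts at day 30 (Section 9.3), t0 = 30/365.25 = 0.082 years; visits at discharge, 3 months and years 1 to 5; exit at the second missed visit (Section 10.7).

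**Assumed.** Constant mortality λ = 4% per year (range 2% to 6%); a share p = 5%, 10% or 20% lost; last attended visit L spread evenly over discharge, 0.25, 1, 2 and 3 years, giving exits E at 1, 2, 3, 4 and 5 years. Time before discharge adds nothing to late time, so L = t0 for the first group. Everyone is taken as alive at t0.

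**Formulas.** S(t) = exp(−λ(t − t0)).
- Subjects not lost: deaths N(1−p)(1−S(5)); years = deaths/λ.
- Lost subjects, N·p/5 in each of five groups: deaths 1−S(L) by the last visit, S(L)−S(E) from there to exit, S(E)−S(5) after exit.

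**At p = 10%.** Not lost: 180 × 0.1786 = 32.14 deaths and 32.14/0.04 = 803.6 years. The 20 lost subjects have 0.91 expected deaths by the last visit, 1.27 from there to exit and 1.40 from exit to year 5.

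| Convention | Deaths / years at 10% lost | Rate, %/yr | Error at 5 / 10 / 20% lost |
|---|---|---|---|
| 1. Deaths and time both end at exit, all deaths to exit known | 34.32 / 858.0 | 4.00 | 0 / 0 / 0% |
| 2. Deaths and time both end at last visit | 33.05 / 826.3 | 4.00 | 0 / 0 / 0% |
| 3. Time runs to exit, deaths between last visit and exit not counted | 33.05 / 859.1 | 3.85 | −1.9 / −3.8 / −8.0% |
| 4. Deaths to exit counted, survivors' time ends at last visit | 34.32 / 827.4 | 4.15 | +1.8 / +3.7 / +8.0% |
| 5. Deaths to year 5 counted, survivors' time ends at exit | 35.71 / 860.0 | 4.15 | +1.9 / +3.8 / +7.9% |
| 6. Deaths to year 5 counted, survivors' time ends at last visit | 35.71 / 831.5 | 4.30 | +3.6 / +7.4 / +15.9% |

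Rows 5 and 6 need a complete search to year 5, which Section 10.7 does not promise. Over 2% to 6% yearly mortality, the errors at 20% lost are −7.8 to −8.1% (row 3), +7.9 to +8.2% (row 4), +7.5 to +8.4% (row 5) and +15.0 to +16.9% (row 6). A simulation on the same visit schedule gives 3.94, 3.85 and 3.69 for row 3 and 4.08, 4.16 and 4.34 for row 5 at 5%, 10% and 20% lost.

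**Scale.** With 35.71 expected deaths the relative standard error is 1/√35.71 = 16.7%.

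**Would one sentence ending deaths and time at exit settle it?** Only if every death up to exit becomes known. Section 10.7 asks for an attempt. Where the attempt fails, the death is missing and the time still counts, which is row 3: 3.93, 3.85 and 3.68% per year.

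**Mortality doubled after the last attended visit (assumed).** The true five-year rates become 4.14, 4.28 and 4.56% per year at 5%, 10% and 20% lost.
- Exit rule, all deaths to exit known: 4.07, 4.14, 4.30, or 1.7%, 3.2%, 5.7% low.
- Exit rule, none of the lost subjects' later deaths known: 3.925, 3.847, 3.681 against 4.138, 4.278, 4.558, or 5.1%, 10.1%, 19.2% low.
- Both ended at last visit: 4.00 throughout; 1 − 4.00/4.138, 1 − 4.00/4.278 and 1 − 4.00/4.558 give 3.3%, 6.5%, 12.2% low.

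No end date is free of bias when loss is related to death.

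**The case for a change.** The strongest case for a change is that the gap is real and cheap to fill. Sections 10.7 and 10.8 sit awkwardly together: exit is when no more data are required, yet a search is ordered afterwards. A short rule that goes by date of death rather than date of discovery, with subjects of unconfirmed status followed only to the date last known alive, returns 4.00% at every loss share when loss is unrelated to death. It could be fixed before anyone sees the data. The gap is also wider than mortality, since the same denominator serves every safety endpoint and no registry search covers non-fatal events. Nor is exit a neutral date for all: Section 10.8 keeps subjects with an explant or a failed implant for 30 days or until their adverse events resolve, so their end of follow-up can depend on outcome.

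The facts in that case stand. Writing the convention down would be tidy, and the two-part rule is better than ending everyone at exit. What does not stand is the step from an unwritten convention to a defect. The two-part rule is what a competent analyst would do with a per-year rate and a Kaplan-Meier curve, and the forms in Appendix 15.3 largely support it. Leaving post-exit deaths out is also the natural reading, since Section 10.7 places the search after termination from the trial. The rule would still be biased low if lost subjects die more often, and biased high if the search finds deaths more readily than it confirms survival.

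**Conclusion.** No change is called for. Section 9.3 omits the end of time at risk and the use of deaths found by the later search, but this is detail that analysts fill sensibly from Sections 10.7 and 10.8 and the forms. Nothing in the plan directs deaths and time to end at different dates. The trial is single-arm and the safety rates are descriptive, so no decision turns on the choice.

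Under the assumed 4% yearly mortality with loss unrelated to death, a mismatched convention moves the rate by under 4% at 5% lost, by at most 7.4% at 10% lost and by at most 15.9% at 20% lost. All of these are below the sampling error of about 17%. Only one case examined exceeds it: 20% lost, mortality doubled after the last visit, and no lost subject's later death known, at 19.2% low. That shortfall comes from deaths nobody has found, and a sentence ending time at exit would leave it in place. Mortality, loss shares, the even spread of loss and the doubling are all assumptions. If loss in this trial proved heavy, the number of subjects with unknown vital status would be needed to interpret the rate.

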9.4 PERFORMANCE ANALYSIS

Hemodynamic Variables

Valvular regurgitation will be summarized by the number and percentage of subjects in each level of regurgitation. Other hemodynamic parameters will be summarized by N, mean, and standard deviation. These summaries will be summarized at baseline and each applicable follow-up visit for all subjects in the investigational valve population, and will be stratified by valve size.

NYHA Class

A comparison of preoperative and postoperative NYHA functional class (presented as the percentage of subjects in each class at baseline, at each follow-up time-point, and as the percentage of subjects at each follow-up time-point who improved, worsened, or did not change in class) will be presented. This comparison will be based on the investigational valve population. Additionally, a cross-tabulation of baseline vs. 1-year NYHA Class will be presented for all subjects in the investigational valve population with both baseline and 1-year NYHA data.

Quality of Life

The number, mean and standard deviation for the Quality of Life (EQ-5D) summary measurement will be presented at the pre-procedure and at the 1-year post procedure follow-up visit. In addition, the number and mean for the change from pre-procedure to the 1-year post procedure follow-up visit will be calculated and presented.

The number, mean, and standard deviation for the SF-12 physical and mental health summary measures (PCS-12 and MCS-12, respectively) will be calculated at the pre-procedure and at the 1-year post procedure follow-up visit. In addition, the number and mean for the change from pre-procedure to the 1-year follow-up in PCS-12 and MCS-12 will be presented.

9.5 OTHER DATA

The mean and standard deviation of blood data will be calculated and presented.

9.6 MISSING DATA

All analyses will apply to any available valid data. No data imputation will be performed for missing data.

10 TRIAL PROCEDURES

Table 3 summarizes all procedures to be conducted during the trial.

Table 3: Summary of Trial Assessments

Trial Procedure	Baseline	Implant	Discharge	3 months	1, 3, 5 year	2 & 4 years
Written Informed Consent	X					
Pregnancy Test	X					
Medical History	X					
Medical Evaluation	X		X	X	X	X
Height	X					
Weight	X		X	X	X	X
12-lead ECG	X		X	X	X	X
NYHA	X			X	X	X
Medications	X		X	X	X	X
Adverse Events		X	X	X	X	X
Echocardiography ¹ (TTE)	X		X	X	X	X ²
Echocardiography ³ (TEE)		X				
Auscultation						X ²
Quality of Life (EQ-5D and SF-12v2) ⁴	X				X	
Blood tests						
Complete Blood Count ⁵	X		X	X	X	X
Plasma free hemoglobin	X		X	X	X	X
Serum Creatinine	X					
Coagulation Profile	X		X	X	X	

Procedure table notes:

- 1 TTE will be the standard echo assessment for the aortic valve
- 2 If murmur heard then echo required
- 3 TEE intra-operatively and within 1 hour (from cross clamp removal) to confirm placement of the device and confirm initial function
- 4 Quality of Life only required at Baseline and at 1-year post-procedure
- 5 Complete blood count includes red blood cells, white blood cells, hemoglobin, hematocrit, platelet count

10.1 BASELINE EVALUATION

10.1.1 SUBJECT SCREENING

All subjects diagnosed with aortic valve disease requiring aortic valve replacement seen by cardiac surgeons participating in this clinical trial should be pre-screened for eligibility. All subjects who meet initial eligibility requirements will be asked to participate. A Screening Log will be provided to the trial sites to maintain a cumulative log of all screened subjects admitted for aortic valve replacement by the cardiac surgeons participating in this trial. For subjects listed as not eligible for participation in the clinical trial, a reason supporting the disqualification of the subject must be entered on the screening log. The Screening Log shall be completed and faxed to the Trial Sponsor regularly (at least once per month). Any subject deemed ineligible due to active endocarditis, recent myocardial infarction, pregnancy or lactating, or due to participation in another clinical trial may be re-screened later. Re-screened subjects must be re-entered on the Screening Log.

10.1.2 INFORMED CONSENT

Subjects who are eligible for participation in the clinical trial shall be provided with patient consent information, approved by the site's ethics committee (EC). Each subject shall be given ample time to read the Informed Consent in its entirety and ask questions to make an informed decision. The subject must sign and date the trial approved Informed Consent prior to participation, i.e. prior to any trial procedures. Subjects who provide informed consent will be assigned a trial subject identification number. The Investigator, or designee, and any witnesses shall also sign and date the consent form, as applicable. Failure to provide Informed Consent renders the subject ineligible for participation in the clinical trial including undergoing treatment with the trial device. Subjects who do not provide informed consent are recorded on the Screening Log.

10.1.3 BASELINE ASSESSMENT

After a written informed consent has been obtained from the subject the following baseline data will be obtained (see **Table 4**); demographic and medical history, 12-lead electrocardiogram (ECG), transthoracic echocardiograph (TTE) per protocol, blood studies per protocol, an assessment of NYHA Functional Classification, Quality of Life (EQ-5D and SF-12v2), and coagulation profile (via INR or PTT). Test results conducted within 30 days before aortic valve surgery may be used for this trial if all values per protocol are available and there has been no significant change in the subject's condition that would affect the test results.

Table 4 Baseline Assessment

Clinical/Physical Assessment		Blood Studies	Echocardiography (TTE)
Date of Assessment	Anti-thromboembolic	Blood Draw Date	Date of Exam
Date of Birth	Therapy	White Blood Cell Count	REFER TO ECHO MANUAL
Sex/Gender	(medications)	Red Blood Cell Count	
Height	Cardiovascular Risk Factors	Hemoglobin	
Weight	Cardiovascular Conditions	Hematocrit	
Heart Rate	Previous Procedures /	Platelet Count	
Blood Pressure	Interventions	Plasma Free	
Cardiac Rhythm (12-lead ECG)	Non-Cardiovascular	Hemoglobin	
NYHA Classification	Conditions	Serum Creatinine	
Quality of Life (EQ-5D & SF-12v2)	Pregnancy Test	Coagulation Profile	

10.2 SURGICAL PROCEDURE

10.2.1 PROCEDURE PREPARATION

The surgical approach used will be at the discretion of the investigator per his/her routine surgical practice. At the time of aortic valve replacement, a transesophageal echocardiogram to further assess the anatomy is recommended prior to aortic valve (to ensure no withdrawal criteria are met per section 8.4). After performing the aortotomy, the native valve and surrounding anatomy should be examined for compatibility with the device again to ensure no withdrawal criteria are met.

10.2.2 MODEL 11000 IMPLANTING PROCEDURE

A detailed description of device preparation and use is provided in the Instructions for Use (IFU), (See Clinical Investigator's Brochure). Investigators must be familiar with Precautions and Implant Technique described in the IFU prior to use of the index valve.

